### 5.3 Criteria for potentially clinically significant and clinically significant abnormal laboratory tests

Hemoglobin A1c criteria is explicitly stated in the table below. For all other parameters, a PCS/CS criterion is met when both of the following occur (baseline refers to ORION-8 baseline):

- There is a post-baseline value that meets the threshold
- The baseline value does not meet the threshold

Some examples are:

- For leukocytes, a subject satisfies “ $\leq 2.8 \times 10^9/L$ ” criterion as long as the baseline value is  $> 2.8 \times 10^9/L$  and any post-baseline value is  $\leq 2.8 \times 10^9/L$ ; a subject satisfies “ $\geq 16 \times 10^9/L$ ” criterion as long as the baseline value is  $< 16 \times 10^9/L$  and any post-baseline value is  $\geq 16 \times 10^9/L$ .
- For CK, a subject satisfies “ $> 3$  and  $\leq 5 \times ULN$ ” criterion as long as the baseline value is  $\leq 3 \times ULN$  and any post-baseline value is  $> 3$  and  $\leq 5 \times ULN$ . A subject satisfies “ $> 5$  and  $\leq 10 \times ULN$ ” criterion as long as the baseline value is  $\leq 5 \times ULN$  and any post-baseline value is  $> 5$  and  $\leq 10 \times ULN$ . If a subject satisfies both “ $> 3$  and  $\leq 5 \times ULN$ ” and “ $> 5$  and  $\leq 10 \times ULN$ ” criteria and does not satisfy the criteria of any more severe category, the subject will be presented under “ $> 5$  and  $\leq 10 \times ULN$ ” but not under “ $> 3$  and  $\leq 5 \times ULN$ ” because the most severe category will be used for CK.
- For serum creatinine, the CS criterion is satisfied if at least one of the following is true:

- The baseline value is  $\leq 2$  mg/dL and any post-baseline value is  $> 2$  mg/dL.
- Any post-baseline value is  $\geq 50\%$  increase from baseline, regardless of whether the baseline value is  $\leq 2$  mg/dL.

Parameter	Unit	Lower Boundary	Upper Boundary
Hematology			
Hematocrit	%	$\leq 0.8 \times \text{LLN}$	N/A
Hemoglobin	g/dL	$\leq 10$ g/dL	N/A
Platelet Count	$10^9/\text{L}$	$\leq 75^*$	$\geq 700^*$
White Blood Cell (Leukocyte) Count	$10^9/\text{L}$	$\leq 2.8$	$\geq 16$
Serum Chemistry			
Alanine Aminotransferase (ALT/SGPT)	U/L	N/A	$> 1$ and $\leq 3 \times \text{ULN}$
Alanine Aminotransferase (ALT/SGPT)	U/L	N/A	$> 3$ and $\leq 5 \times \text{ULN}^*$
Alanine Aminotransferase (ALT/SGPT)	U/L	N/A	$> 5$ and $\leq 10 \times \text{ULN}^*$
Alanine Aminotransferase (ALT/SGPT)	U/L	N/A	$> 10$ and $\leq 20 \times \text{ULN}^*$
Alanine Aminotransferase (ALT/SGPT)	U/L	N/A	$> 20 \times \text{ULN}^*$
Alkaline Phosphatase	U/L	N/A	$> 2 \times \text{ULN}^*$
Aspartate Aminotransferase (AST/SGOT)	U/L	N/A	$> 1$ and $\leq 3 \times \text{ULN}$
Aspartate Aminotransferase (AST/SGOT)	U/L	N/A	$> 3$ and $\leq 5 \times \text{ULN}^*$
Aspartate Aminotransferase (AST/SGOT)	U/L	N/A	$> 5$ and $\leq 10 \times \text{ULN}^*$
Aspartate Aminotransferase (AST/SGOT)	U/L	N/A	$> 10$ and $\leq 20 \times \text{ULN}^*$
Aspartate Aminotransferase (AST/SGOT)	U/L	N/A	$> 20 \times \text{ULN}^*$
Creatine Kinase (CK)	U/L	N/A	$> 1$ and $\leq 3 \times \text{ULN}$
Creatine Kinase (CK)	U/L	N/A	$> 3$ and $\leq 5 \times \text{ULN}$
Creatine Kinase (CK)	U/L	N/A	$> 5 \times$ and $\leq 10 \times \text{ULN}^*$
Creatine Kinase (CK)	U/L	N/A	$> 10$ and $\leq 20 \times \text{ULN}^*$
Creatine Kinase (CK)	U/L	N/A	$> 20 \times \text{ULN}^*$
Hemoglobin A1C	%	N/A	$\geq 6.5\%$ and $\geq 0.5\%$ change from baseline
Serum Creatinine	mg/dL	N/A	$\geq 50\%$ increase from baseline or $> 2$ mg/dL*
Total Bilirubin	mg/dL	N/A	$> 2 \times \text{ULN}^*$
LLN: Lower limit of the standard reference (normal) range; ULN: Upper limit of the standard reference (normal) range. For AST, ALT and CK, the most severe result for each subject will be used. *Clinically significant laboratory boundaries.			

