10.3 Statistical Analyses

10.3.1 Demographic and Background Characteristics

Subject demographics and baseline characteristics except age collected from prior corresponding Phase III studies for each subject will be used for the summary using the safety population. For subjects moved over from the Phase II ORION-3 study, subject demographics and baseline characteristics collected at the ORION-3 study baseline will be used for this summary. Age will be recalculated by adding the duration that each subject spent in the prior corresponding Phase II or Phase III study

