10.3.4.2 Laboratory Tests

Laboratory values will be summarized at each time point. Analyses will also be performed for each lab parameter for incidence rates of potentially clinically significant (PCS) values for subjects without PCS value at baseline (defined as baseline in the corresponding Phase II or Phase III feeder study), as well as without PCS value at Day 1 of the study

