### 1.1 Study design

This study will be a long-term extension of the Phase II lipid lowering trial CKJX839A12201E1 (ORION-3; MDCO-PCS-16-01), which is the extension study of CKJX839A12201 (ORION-1; MDCO-PCS-15-01), and Phase III lipid-lowering studies CKJX839A12303 (ORION-9; MDCO-PCS-17-03), CKJX839A12304 (ORION-10; MDCO-PCS-17-04), and CKJX839A12305 (ORION-11; MDCO-PCS-17-08). This trial will be a global, multicenter study in approximately 300 centers. Up to 3300 subjects with atherosclerotic cardiovascular disease (ASCVD), ASCVD-risk equivalents (e.g., diabetes and familial hypercholesterolemia), or heterozygous familial hypercholesterolemia (HeFH) and elevated LDL-C despite treatment with LDL-C lowering therapies who are eligible and willing to participate may be enrolled. The objective of the study is to evaluate the efficacy, safety, and tolerability of long-term dosing of inclisiran. Informed consent will be obtained from subjects before the initiation of any study-specific procedures. The End of Study (EOS) visit in the previous feeder studies will be Day 1 in this extension trial except for subjects enrolled in Sweden. Sweden Specific Protocol Amendment 1 (to Global Amendment 1 version, dated 1 Nov 2018) was implemented to allow limited lab tests to be done on Day 1 and to collect any safety information during the gap between feeder's EOS and Day 1 of this study until ethics committee approval was granted in that country.

Subjects rolled over from the Phase III studies (ORION-9/10/11) will receive blinded inclisiran sodium 300 mg which is equivalent to 284 mg inclisiran, or blinded placebo on Day 1 in this trial. Subjects who received placebo in the previous Phase III feeder studies will receive blinded inclisiran and subjects who received inclisiran in the previous Phase III feeder studies will receive blinded placebo at this visit, in order to

- maintain the blinding of the feeder studies until database lock of those studies,
- maintain the semi-annual dosing schedule for subjects who received inclisiran in the previous Phase III feeder studies,

- administer the first two doses of inclisiran on the three-monthly initial dosing schedule for subjects who received placebo in the previous Phase III feeder studies.

All subjects will return at Day 90 for the next visit and will receive open label inclisiran sodium 300 mg.

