## Feeder study baseline

When it refers to a timepoint, feeder study baseline is defined as the date/time of first study drug administration in ORION-1/9/10/11.

When it refers to a laboratory parameter baseline, it is defined as the last available record with date/time  $\leq$  date/time of feeder study baseline as defined above, unless otherwise specified. When time is not available for baseline or for the laboratory assessment, the comparison of date/time will be based on the date only. The same rule is applicable throughout this document to determination of chronological orders, unless otherwise specified.

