### 2.7.3.1 Summary tables using descriptive statistics

Summaries for safety laboratory values will include observed value, changes and percent changes from ORION-8 baseline over time:

- Hematology and coagulation parameters will be summarized at ORION-8 baseline (for observed value only), at Day 1080, and at EOS.
- Safety chemistry parameters in the full serum chemistry panel but not in limited serum chemistry panel will be summarized at ORION-8 baseline (for observed value only), at Day 1080, and at EOS.
  - These include direct and indirect bilirubin, lactate, bicarbonate, uric acid, urea (blood urea nitrogen; BUN), sodium, potassium, calcium, inorganic phosphorus, chloride, albumin, total protein, fasting glucose.
- Safety chemistry parameters in limited chemistry panel, which is a subset of the full chemistry panel, will be summarized at ORION-8 baseline (for observed value only), at each scheduled visit from Day 90 to Day 1080, and at EOS.
  - These include aspartate aminotransferase (AST), alanine aminotransferase (ALT), alkaline phosphatase (ALP), gamma glutamyl transferase (GGT), total bilirubin (TBIL), creatine kinase (CK), creatinine, eGFR, glycated hemoglobin A1C (HbA1c).

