### 2.7.3.3 Clinically significant laboratory values

The number and percentage of subjects with potentially clinically significant (PCS) laboratory values or clinically significant (CS) laboratory values (refer to [Appendix 5.3](#) for the criteria) will be summarized. For AST, ALT and CK, the most severe result for each subject will be used. For creatinine, the following two categories will also be presented in addition to the CS criterion:

- 1) Subjects with the baseline value  $\leq 2$  mg/dL and any post-baseline value  $> 2$  mg/dL.
- 2) Subjects who are not in the first category but has  $\geq 50\%$  increase from baseline.

For liver chemistry parameters (ALT, AST, ALP, TBIL), the number and percentage of subjects whose PCS/CS value returned to baseline level at the last measurement will also be summarized. Here the baseline level is defined as a value of the same category as the baseline category or a value of a better category than the baseline. For example, if a subject's baseline ALT is  $>3$  and  $\leq 5$  x ULN and the subject's ALT elevated to  $>5$  and  $\leq 10$  x ULN at the worst measurement post baseline, the subject is considered to have returned to baseline level at the last measurement if the last ALT value of that subject is  $\leq 5$  x ULN.

Listings of all subjects with PCS or CS laboratory values will be presented. Subjects will appear once per lab parameter but may appear under multiple lab parameters.

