## **4 Change to protocol specified analyses**

No change from protocol specified analysis was made.

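### The protocol conditions PCS laboratory incidence on feeder-study baseline as well as Day 1; the SAP uses ORION-8 baseline only, with a different denominator, and declares no change

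*SAP*

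**What the plan says.** Protocol 10.3.4.2 asks for PCS incidence, parameter by parameter, and limits it to those "without PCS value at baseline (defined as baseline in the corresponding Phase II or Phase III feeder study), as well as without PCS value at" (the second reference point being Day 1). Two reference points are named, and both describe who is at risk.

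SAP 2.7.3.3 plans to summarise "The number and percentage of subjects with potentially clinically significant (PCS) laboratory values or clinically significant (CS) laboratory values" and sends the reader to SAP 5.3 for the criteria. There, for every parameter except HbA1c, "a PCS/CS criterion is met when both of the following occur (baseline refers to ORION-8 baseline": a post-baseline value meets the threshold and the baseline value does not. The HbA1c row refers to a change from baseline without naming which one.

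SAP 2.1.1 does define a feeder reference: "feeder study baseline is defined as the date/time of first study drug administration in ORION-1/9/10/11". SAP 2.6.1 uses it for the lipid endpoints. Nothing in SAP 2.7.3.3 or 5.3 uses it for PCS or clinically significant (CS) values.

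SAP 2.1 bases percentages on subjects in the analysis set with non-missing data unless a section says otherwise. SAP 4 states: "No change from protocol specified analysis was made".

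**The concern.** The baseline condition decides which subjects count as laboratory safety cases. The feeder reference in the protocol looks deliberate: section 10.3.4.1 uses Day 1 alone for treatment-emergent adverse events, and the next subsection names feeder baseline and Day 1 separately for laboratory values. SAP 1 states that the SAP was prepared from the same protocol version (global amendment 2), so this is not a leftover from superseded text.

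ORION-8 baseline precedes inclisiran in only one of the three reporting groups, Phase III Placebo-Inclisiran. In the other two it is a value obtained after inclisiran treatment. Measuring new abnormalities only from that point answers a narrower question than the safety of long-term use, and a reader who trusts SAP 4 would not know that the reported incidence is not the one the protocol defined.

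**Working it through.** The plan gives no figure to reproduce, so the check sets the texts side by side.

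**1. The two specifications**

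| Element | Protocol 10.3.4.2 | SAP 2.7.3.3, 5.3 and 2.1 |
|---|---|---|
| Reference | Feeder baseline, as well as Day 1 | ORION-8 baseline only |
| Role of the condition | Restricts the subjects at risk | Part of the event definition |
| Denominator | Subjects without the PCS value | By default, all with non-missing data |

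**2. Who is counted.** Let F = 1 if the subject is beyond the threshold at feeder baseline and D = 1 if so at Day 1. Assume that events are values after Day 1 and that every subject below has one.

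| (F, D) | SAP | Two analyses: Day 1 table | Two analyses: feeder table | One joint condition |
|---|---|---|---|---|
| (0,0) | yes | yes | yes | yes |
| (1,0) | yes | yes | no | no |
| (0,1) | no | no | yes | no |
| (1,1) | no | no | no | no |

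On the two-analysis reading, pattern (0,1) appears in no planned PCS/CS table. On the joint reading nothing is masked, but the SAP adds pattern (1,0).

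**3. Percentages.** Let N be the subjects with non-missing data, d those already beyond the threshold at ORION-8 baseline, and x those who cross it later.

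- Protocol, Day 1 condition: x / (N − d).
- SAP default: x / N.
- Ratio of SAP to protocol: (N − d) / N = 1 − d/N.

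The numerators agree, but the SAP percentage is lower whenever d and x are above 0. On the joint reading the SAP has a numerator and a denominator each at least as large as the protocol's, so its percentage may be higher or lower.

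**4. Timing of ORION-8 baseline.** Protocol 6 places Day 90 at 180 days after the last feeder injection for subjects who had inclisiran. Day 1 is therefore nominally 180 − 90 = 90 days after a dose for Phase III Inclisiran-Inclisiran; subjects with a gap before Day 1 differ. Footnote 10 to protocol Table 6-1 says that ORION-3 subjects were all on inclisiran in the feeder trial.

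**5. Scope.** Boundaries in the SAP 5.3 table, with the two-part creatinine criterion counted once:

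- Hematology: hematocrit 1 + hemoglobin 1 + platelets 2 + leukocytes 2 = 6.
- Chemistry under the ORION-8 rule: ALT 5 + AST 5 + CK 5 + ALP 1 + creatinine 1 + bilirubin 1 = 18.
- Total under the rule: 6 + 18 = 24; with HbA1c, 25.

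Protocol Table 6-1 schedules hematology once after Day 1, at EOS. SAP 2.7.3.1 agrees: "Hematology and coagulation parameters will be summarized at ORION-8 baseline (for observed value only), at Day 1080, and at EOS". The chemistry parameters are scheduled up to 6 dosing visits + EOS = 7 times, fewer for ORION-3 rollovers. On the two-analysis reading, losing a hematology case at scheduled visits needs a value beyond the threshold at both Day 1 and EOS. ALT, AST and CK can still count at a higher grade where one exists, and creatinine can count on a further rise of at least 50%. The loss is therefore at the given threshold, not of the subject altogether.

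**The case against.** The study is descriptive and non-comparative, so no error rate or power is at stake, and a Day 1 reference matches the protocol's own rule for treatment-emergent events. In Placebo-Inclisiran, ORION-8 baseline precedes the first inclisiran dose, and a feeder-baseline table would there also pick up abnormalities that began on placebo. SAP 2.7.3.4 adds a Hy's Law summary that ignores baseline, so the joint liver signal is kept. All of this stands. It shows that an ORION-8 reference is defensible if declared; it does not make SAP 4 accurate. Protocol 10 leaves detailed specification to the SAP, but dropping a stated condition is not added detail.

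Four inferences go further than the documents allow.

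- A reader might conclude that the SAP hides inclisiran toxicity. Masking follows only on the two-analysis reading, and as a drug question only in the two groups already treated. The joint reading gives extra counts instead.
- A reader might take the SAP table to be the protocol's Day 1 table. Only the numerators match.
- A reader might rely on exclusion criterion 4 to rule out raised liver values at Day 1. It refers to the last recorded feeder visit before study entry and, for ALT and AST, to unexplained elevations; the worked example in SAP 2.7.3.3 itself has a baseline ALT above 3x ULN.
- A reader might say that feeder baseline is undefined for ORION-3 rollovers, because for them protocol 10.3.1 says "subject demographics and baseline characteristics collected at the ORION-3 study baseline will be used for this summary". That section covers demographics and baseline characteristics. SAP 2.1.1 expressly goes back to ORION-1; SAP 1.1 describes ORION-3 as a trial "which is the extension study of CKJX839A12201 (ORION-1; MDCO-PCS-15-01". The protocol's phrase about the corresponding Phase II study fits this loosely, but the SAP's choice is stated.

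**Conclusion.** The point holds. The SAP omits the protocol's feeder-baseline condition for PCS/CS laboratory incidence, uses a different denominator by default, and states that nothing changed. The statement in SAP 4 is wrong on either reading of protocol 10.3.4.2. The direction of the effect depends on the reading: a missing table and uncounted persistent abnormalities if two analyses were meant, extra cases if one joint condition was meant.

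The rule reaches 24 of 25 boundaries, which measures scope and not impact. The documents give no PCS rates, so neither the number of subjects affected nor d/N can be stated. The conclusion assumes that incidence is counted on values after Day 1 and that the default percentage base in SAP 2.1 applies, since SAP 2.7.3.3 and 5.3 set no other. It should be fixed because it concerns a primary-objective safety output and the change is cheap; no inferential result depends on it.

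**What to change.** In SAP 2.7.3.3 and 5.3:

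1. State whether protocol 10.3.4.2 means two analyses or one joint condition.
2. If two, add PCS/CS incidence tables by feeder treatment group for subjects without the PCS/CS value at feeder-study baseline as defined in SAP 2.1.1, beside the ORION-8-baseline tables. If one, apply both conditions together.
3. Set each denominator, including that of the existing ORION-8 table, to subjects without the PCS/CS value at the relevant baseline.
4. Footnote any feeder-baseline table to say that Placebo-Inclisiran counts include abnormalities that began on placebo.
5. Name the baseline in the HbA1c row (editorial; SAP 2.7.3.1, 2.7.4.1 and 2.7.4.3 already point to ORION-8 baseline).

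In SAP 4, list any departure that remains, with its reason.

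The cost is SAP wording and one repeat set of descriptive tables; the SAP history places this version before database lock. One check comes first: protocol 9 mentions importing data from ORION-3, ORION-9, ORION-10 and ORION-11 but not ORION-1, so the availability of ORION-1 safety laboratory values for ORION-3 rollovers should be confirmed.
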